Aim 1: Evaluate recruitment feasibility and participant acceptability and characteristics in a pilot RCT of CCT vs. TAU in Veterans who previously engaged in PTSD treatment and report current cognitive functioning deficits. **Aim 2:** Estimate effect sizes to calculate needed sample size for a fully powered RCT of CCT vs. TAU for improving objective and subjective cognitive functioning deficits, mental health, other aspects of functioning, and QOL.

5

Study Design: The proposed study is a single site, pilot RCT comparing 10-session CCT (one session per week) to 10 weeks of TAU as the control condition.

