Intervention: TAU will consist of routine, weekly mental health psychotherapy as all participants must have a referring mental health provider to be eligible for this pilot RCT. The CCT rehabilitation model aims to teach individuals strategies that allow them to work around cognitive deficits. CCT provides training in compensatory attention and learning/memory skills, formal problem-solving strategies applied to daily problems, and the use of external aids, such as calendar systems and assistive devices to promote completion of daily tasks ([name] et al., 2016). CCT sessions consists of interactive didactic information and discussion, and activities that introduce a variety of cognitive strategies and external aids. Participants are given a copy of the treatment manual and a paper calendar or day planner if requested, or they may request training on a smartphone or electronic calendar system instead. They will receive extensive graduated training in and practice with their chosen calendar system across sessions with a focus on how the day planners can facilitate the use of compensatory strategies taught each week. [name] will supervise the CCT groups run by the study coordinator, co-facilitating early groups as needed for training purposes. They have an ongoing relationship with local psychology doctoral programs which may provide clinical trainees who may provide supervised group facilitation. The current CCT Treatment Manual ([name], [name], et al., 2016) is included as an Appendix, though aspects of structure and content will be changed before this pilot RCT for PTSD to tailor the intervention to PTSD rather than TBI. We have successfully tailored CCT to other similar Veteran populations in the past, and we expect to be able to refine it for Veterans with PTSD prior to CDA initiation. We have also had success training a variety of master's level research associates and providers to administer the intervention, and similar training and fidelity monitoring protocols (e.g., recorded sessions, 20% random fidelity checks) previously utilized by Drs. [name], [name], and [name] will be implemented in this proposed efficacy study. The following table outlines the CCT structure and content.

Table of CCT for PTSD Session Content				
Session	Major Concepts	Examples of Strategies	Session Activities	Home Exercise
1	Intro and PTSD/cognitive functioning psychoeducation	Creating a "home" for important items	Day planner use	Finding a home for the day planner

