intervention fidelity; and maximize participant retention. Detailed records on recruitment, session attendance, and homework completion will be kept throughout the intervention. Consistent with Consolidated Standards of Reporting Trials (CONSORT) guidelines, we will obtain data to determine (1) the number of participants who reported moderate or greater symptom ratings, or who have impairments in one or more cognitive domain, from the baseline assessment; (2) the number of participants referred to the study, (3) the number of participants screened by research staff for study eligibility, and (4) the number enrolled in and completing all aspects of the study including treatment sessions and assessments. We will ascertain reasons for unsuccessful recruitment, ineligibility, and unsuccessful enrollment of eligible Veterans. In addition, we will collect data on the intensity of outreach needed to recruit and enroll participants (e.g., number of phone calls required before Veterans complete eligibility screening, number of "no shows" for eligibility screening appointments) and length of time between initial recruitment attempt, eligibility screening, and completion of the pre-intervention assessment. Participant Retention will be measured by the proportion of participants who complete follow-up assessments within two weeks of the target date. Treatment satisfaction will be assessed by the Client Satisfaction Questionnaire (CSQ8).

Functional and Clinical Variables: We will use similar assessment procedures as in the Aim 1 study to assess cognitive and functional domains most strongly associated with PTSD (details listed in the table below). We will examine sleep and mental health symptoms (including PTSD and depression) not directly targeted by CCT to examine comparability to TAU. Assessments will take approximately 1.5 hours and will occur at baseline, post-treatment, and 6-month follow-up for both groups.

Measure	Construct Assessed			
Objective Cognitive Functioning (Neuropsychological Tests)				
Test of Premorbid Functioning (ToPF)	Verbal abilities; estimate of premorbid cognitive functioning			
California Verbal Learning Test (CVLT-II; Delis et al., 2000)	Verbal learning and memory, forced choice validity			
Wechsler Adult Intelligence Scale (WAIS-IV) Digit Span & Coding subtests (Wechsler, 2008)	Attention, working memory, processing speed, reliable digit span validity			

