Enrollment and Assessment Procedures: Prior to enrollment, interested Veterans will be prescreened. The study coordinator will conduct a medical record review to document cognitive symptoms, medical and psychiatric history, and recent treatments and medications. The Neurobehavioral Symptom Inventory (NSI) will be used as a screening tool to determine the presence of moderate or greater cognitive symptoms for eligibility purposes. A brief phone interview will ensure that Veterans are interested in participating and meet eligibility criteria. All participants will be screened to ensure their ability to comprehend study procedures, risks and benefits. We anticipate that up to 500 Veterans will need to be screened in order to achieve the desired sample size of 36-48 Veteran participants in the study. Veterans will be provided the opportunity to have the informed consent materials mailed to them. After the Veteran receives the informed consent materials, a trained study team member will call the Veteran to go through the informed consent procedures and answer any questions. If the Veteran chooses to participate, he or she will sign the informed consent documents and mail them back to [name] using a pre-addressed and stamped envelope. The study assessment will only be scheduled after the hard copy informed consent is received back from the Veteran. Following determination of eligibility, provision of informed consent, and enrollment into the pilot trial, Veterans will initiate the pilot RCT assessments, and, when assigned to the CCT condition, the 10-week CCT group intervention (weeks 2-11). Cognitive assessments and symptom questionnaires will be completed at baseline, post-treatment (approximately 3-months following baseline), and follow-up (6-months following baseline). Veterans will have the option to complete all study activities, including the 10-week CCT intervention and the 3 cognitive assessments via the VA's telehealth system, VA Video Connect (VVC), or via telephone.

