to complete follow-up assessments, advance participant reminders of upcoming assessments, scheduling assessments near the target date at times that are convenient for participants, providing reminder calls 1-3 days prior to the scheduled assessment, and promptly rescheduling missed assessment appointments. We will attempt to retain all enrolled Veterans in the study, regardless of ongoing participation in CCT or other interventions as part of TAU. In our prior research, all Veterans who initiated CCT completed the intervention. For Veterans who discontinue treatment and who express discomfort returning to the clinic to complete follow-up assessments, accommodations will be made to ensure Veterans have the opportunity to continue study participation (e.g., assessment completion via VVC or telephone or at other VAPORHCS locations). We will ensure that participants are appropriately reimbursed for time and travel, paying participants \$50 for each assessment. Recent trials of CCT in VA clinics conducted by Drs. [name], [name], and [name] have exceeded 90% retention.

Inclusion/Exclusion Criteria

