The proposed study poses no serious risks to participants. The study involves direct contact with participants, and there is a slight risk that participants could become upset during groups or assessments or while completing questionnaires. There is also a slight risk that a Veteran could report suicidal thoughts during these contacts, although clinician-patient discussions about mental health or possible suicidal ideation have not been shown to increase the risk of suicide attempts. Participants will be participating in an intervention that has been shown to be acceptable to similar Veteran patients (e.g., those with TBI history), and effective for reducing cognitive problems; however, it is possible that the intervention will not be effective with this population or will produce iatrogenic effects. The risk to participants is minimal but may include breach of confidentiality via inadvertent disclosure of PHI and identifiers and distress upon participating in the CCT intervention.

Protection Against Risk & Participant Safeguards:

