We are also asking participants to allow their data and contact information including identifiers to be stored ('banked") in the Neuropsychology Data Repository (MIRB# 3508) located at the VA Portland Health Care System (VAPORHCS) and managed by [name] [name]. These data will include data resulting from the cognitive test battery and identifiers including name, telephone number, the last four digits of social security number, and study participation dates that will be used in future research. Contribution to the repository is optional.

Transfer of Data Ownership

N/A

Data and Safety Monitoring Plan (DSMP)

Safety Monitoring: The PI or anyone else who has contact with study participants during study activities have the responsibility to monitor for any potential adverse events and protocol

17

deviations. Any adverse participant event will be reported immediately to PI [name], who will contact the participant and determine if additional intervention is needed to ensure participant safety. Protocol deviations will also be immediately reported to [name] who will ensure that adverse events deemed to be unanticipated problems and protocol deviations are properly reported to the IRB in a timely manner. Detailed written documentation will be kept for all adverse events that occur over the course of the study. PI [name] holds weekly meetings with lab personnel where they will discuss adverse events and protocol deviations associated with this project and ways to reduce repeat occurrences. Research staff will examine all cumulative adverse events quarterly to determine if there are any systematic problems and to implement protocol corrections as needed after receiving IRB approval.

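### Adverse events are not asked about on a common schedule, so counts by arm would over-represent CCT, which has 12 scheduled post-baseline study contacts against 2 for TAU

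*Combined protocol and SAP*

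**What the plan says.** Detection of adverse events is described in one place, the Safety Monitoring paragraph of the Data and Safety Monitoring Plan: "The PI or anyone else who has contact with study participants during study activities have the responsibility to monitor for any potential adverse events". Events go at once to the principal investigator and are documented in writing. The review rule is: "Research staff will examine all cumulative adverse events quarterly to determine if there are any systematic problems". The protocol gives no adverse-event question, checklist, recall period or follow-up chart review for either arm. The Protected Health Information section describes the use of medical records for finding participants and confirming eligibility; detecting events is not mentioned.

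Contact with the study differs by arm. Study Design describes a trial "comparing 10-session CCT (one session per week) to 10 weeks of TAU as the control condition". The CCT groups are run by study staff (Intervention). On the control arm, the same section says: "TAU will consist of routine, weekly mental health psychotherapy as all participants must have a referring mental health provider". That care comes from the Veteran's own provider, who is given no duty to report events to the study. Assessments are common to the arms: they "will occur at baseline, post-treatment, and 6-month follow-up for both groups", at about 3 and 6 months after baseline (Enrollment and Assessment Procedures). Retention activities include "providing reminder calls 1-3 days prior to the scheduled assessment".

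On possible harm, Risks and Side Effects says that "it is possible that the intervention will not be effective with this population or will produce iatrogenic effects".

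**The concern.** If events come to light only when a Veteran meets study staff, the number recorded depends on how often they meet as well as on how often events occur. The contact difference is built into the design and falls in the treatment period, when CCT could cause harm. A log filled mainly from CCT sessions would point towards CCT at the quarterly review without any true difference. A table of events by arm, in a report of the pilot or in planning the full trial, would carry the same distortion. Events in TAU Veterans that nobody on the study happens to hear of would be missing from it.

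**Working it through.** The plan states no adverse-event rate or count, so there is no figure to reproduce. The check has two steps.

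**1. Scheduled contacts after baseline**

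- CCT sessions: 10, one per week, in weeks 2 to 11 (Study Design; Enrollment and Assessment Procedures).
- Post-baseline assessments: 2 in each arm, from "Cognitive assessments and symptom questionnaires will be completed at baseline, post-treatment (approximately 3-months following baseline), and follow-up (6-months following baseline").
- CCT: 10 + 2 = 12. TAU: 0 + 2 = 2.
- Before the post-treatment assessment: 10 v 0. From that assessment on: 2 v 2.
- Reminder calls are made in both arms, but the number per assessment is not given. Assuming one call per post-baseline assessment: CCT 12 + 2 = 14, TAU 2 + 2 = 4.

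**2. Effect on recorded events at equal true risk**

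Let q be the chance that an event is noticed at one contact, and k the number of contacts. If each contact is an independent chance to notice the event, the probability that it is recorded is 1 − (1 − q)^k. The documents do not give q, so it is varied. Full session attendance is assumed, and every contact is taken as an opportunity to notice the event.

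Example at q = 0.10: CCT 1 − 0.9^12 = 0.718; TAU 1 − 0.9^2 = 0.190; ratio 0.718 / 0.190 = 3.8.

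| q (assumed) | CCT, k = 12 | TAU, k = 2 | Ratio 12 v 2 | Ratio 14 v 4 |
|---|---|---|---|---|
| 0.05 | 0.460 | 0.098 | 4.7 | 2.8 |
| 0.10 | 0.718 | 0.190 | 3.8 | 2.2 |
| 0.30 | 0.986 | 0.510 | 1.9 | 1.3 |
| 0.50 | 1.000 | 0.750 | 1.3 | 1.07 |
| 0.80 | 1.000 | 0.960 | 1.04 | 1.0 |
| 1.00 | 1.000 | 1.000 | 1.0 | 1.0 |

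In this model CCT is over-recorded at every q below 1, and the excess becomes negligible once q is about 0.80 or more.

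**With a common inquiry.** If events are compared only on a question asked at the two post-baseline assessments in both arms, k is 2 in each arm. The ratio is then 1.0 for any q, provided the question is put in the same way to both arms.

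**The case against.** The strongest reply is that the plan makes no such comparison. Neither the aims nor the Data Analysis section contains a between-arm analysis of adverse events, and the quarterly review is cumulative with no mention of arm. That stands, and it limits the point to any tabulation by arm and to how the cumulative review is read. It does not remove the point, because that review looks for systematic problems and can lead to protocol corrections.

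A reader might infer that every comparison of harms in this trial is biased against CCT, or that the trial could not tell an iatrogenic effect from closer observation. The documents do not support either inference. PTSD, depression and sleep measures are taken at the same visits in both arms (Functional and Clinical Variables), and changes are compared across groups (Clinical and Functional Outcome Analyses). Worsening on those scores would show whatever the number of sessions. Such scores do not record discrete events between visits, and the point is confined to those.

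It can also be said that nothing forbids a TAU provider or a Veteran from reporting an event, that all events are to be documented, that progress notes are among the information collected, and that a data safety monitoring board will be set up. All true. But none of this text provides a way of finding events that study staff did not see. TAU Veterans are in weekly psychotherapy, so the gap is in study recording and not in care. The difference in contact is also confined to the treatment period; the interval between the post-treatment and 6-month visits is equally unobserved in both arms.

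**Conclusion.** The concern holds in a limited form. Detection is passive and tied to study contact, and scheduled post-baseline contacts are 12 v 2 (14 v 4 with one assumed reminder call per assessment). Spontaneously noticed events counted by arm would therefore be expected to favour TAU at equal true risk.

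The direction follows from the schedule. The size does not, because it rests on an unstated q, on full attendance and on contacts acting independently. Over q from 0.05 to 0.80 the recorded ratio runs from 4.7 to 1.04, or from 2.8 to 1.0 with reminder calls. A reader might take the contact ratio, 12 / 2 = 6, as the size of the bias. It is only the limit of the model as q approaches zero, and nothing in the documents puts q there.

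The screening, enrolment and retention criteria and the symptom comparisons are untouched. This is a cheap improvement and not a flaw in the trial's main aims.

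**What to change.** In the Safety Monitoring paragraph of the Data and Safety Monitoring Plan:

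1. Add one fixed set of adverse-event questions at the existing post-treatment and 6-month assessments in both arms, covering the interval since the last assessment. Ask them in the same words of everyone. This matters because the Randomization and Blinding section allows that the assessor may also co-facilitate CCT groups and so know of some events already.
2. Tag each event in the log by source: assessment or CCT session. An event found at a session and also reported at the assessment carries both tags.
3. Base any tabulation by arm on the assessment source only.
4. List events found only at CCT sessions separately, and go on reporting and acting on them as now.

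The cost is a few minutes in each assessment of about 1.5 hours, one column in the log and a short amendment. Recall over the interval will miss some minor events, but the recall interval is the same in both arms.

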Appendix - Supporting Documents List

- CCT Manual
- Phone/In Person Recruitment Script
- Email Message for Recruitment
- Participant Recruitment flyer

21
